6.8 Statistical / Analytical Issues

6.8.1 Handling of Dropouts or Missing Data

The data are analyzed utilizing the last observation carried forward (LOCF) technique to impute the missing data.

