1.4 Potential Risk and Benefit

1.4.1 Potential Risk

The toxicological profile of PDC-1421 was characterized in single and repeat oral dose studies of up to 90 days in rats and repeat oral dose studies of up to 28 days in dogs. Genetic toxicology and safety pharmacology have also been conducted. PDC-1421 was observed to be associated with some adverse effects in serum electrolytes and GI function, but none were clinically significant. Therefore, potential risks of PDC-1421 are fluctuated electrolyte level and gastrointestinal discomfort. We monitored these in the Phase I and Phase II study in MDD and ADHD patients, and there was no deviation of electrolyte level. But there were more gastrointestinal discomfort, such as dry mouth, comparing to the placebo during monitoring in the clinical trial. However, there were non-clinically significant mild lower diastolic blood pressure and lower heart rate in dog telemetry study, and it has been only with the 2500 mg/kg, which is around the NOAEL for dogs. The cardiovascular systems will be monitored in the clinical study.

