5.2 Treatment Schedule

Potential subjects will be introduced by Investigator or his/her designee of the study design at Screening. If the subject agrees to participate and signs the consent form, the screening process will begin. Suitability of the subject will be evaluated by inclusion/exclusion criteria.

Subjects met eligibility criteria will be assigned with a random number to be allocated into 3 treatment groups on a 1:1:1 basis and treated as following dose regimen:

- **Placebo:** 2 placebo capsules thrice daily for 56 days (8 weeks).
- **Low-Dose:** 1 placebo capsule and 1 PDC-1421 Capsule, thrice daily for 56 days (8 weeks).
- **High-Dose:** 2 PDC-1421 Capsules thrice daily for 56 days (8 weeks).

Subjects will be assessed biweekly (Visit 3, 4, 5, and 6). After the end of study treatment, subjects will be requested to return after two weeks for a follow-up (Visit 7). Screening, safety and efficacy assessments will be performed as [Table 15](#).

During the COVID-19 public health emergency or similar events, the assessments of CAARS-S:S, CGI, ADHD-RS-IV, E-SCT, C-SSRS, AE evaluation, Concomitant Medication, Physical examination and Vital sign can be conducted by telephone, video, or email, but those remote assessments should be documented. All COVID-related changes will be pre-approved by the applicable IRBs.

Table 15. Part II-schedule of assessments

	Screening	Treatment Period					Follow-up
Visit	1	2	3	4	5	6	7
*Week	-2 to 0	0	2	4	6	8	10
Informed consent	√						
Subject information	√						
Medical history	√						
DSM-5	√						
CAARS-S:S	√	√	√	√	√	√	√
CGI- S	√	√					
CGI- I			√	√	√	√	√
ADHD-RS-IV	√	√	√	√	√	√	√
E-SCT	√	√	√	√	√	√	√
C-SSRS	√	√	√	√	√	√	√
Concomitant medication	√	√	√	√	√	√	√
Physical examination	√					√	
Vital sign	√	√	√	√	√	√	√
ECG	√					√	
Laboratory examination							
Pregnancy test	√						√
Hematology	√	√		√		√	
Blood chemistry	√	√		√		√	
Eligibility evaluation	√						
Drug accountability		√	√	√	√	√	
AE/SAE evaluation		√	√	√	√	√	√

*On ±2 days.

**If the interval of visit 1 and visit 2 is within 7 days, Hematology and Blood chemistry test of visit 2 can be skipped.

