5.2.2 Part II.- Treatment Period (Visit 2~6)

Subjects who meet the eligibility criteria will be enrolled and take study drugs. At visits 2 to 5, each subject will be dispensed a supply of study drug sufficient for next 2-week treatment period. The subjects will be instructed to take one dose (i.e., two capsules) after a meal thrice daily. Drug compliance is important for the safety and efficacy evaluations. Study coordinator needs to make sure drug adherence of the subjects is at least

80% during the treatment period. Otherwise, study coordinator(s) must report a protocol deviation including lower than 80% compliance and over 100% compliance during the treatment period. At visits 2, 3, 4, 5 and 6, the safety and efficacy parameters will be evaluated by the following items. Baseline data will be collected before dosing study drug.

- Physical examination: skin, head, neck, eyes, ears, nose, throat, heart, lungs, abdomen (liver, spleen), neurological examination, lymph node and extremities.
- Vital sign: heart rate, blood pressure, body temperature
- ECG (Only at visit 6)
- Hematology: RBC, WBC, platelets, hematocrit, hemoglobin, prothrombin time (PT), partial thromboplastin time (aPTT). (Only at visit 2, 4 and 6)
- Blood chemistry: AST, ALT, LDH, total bilirubin, BUN, serum creatinine, free thyroxine (FT4), TSH, sodium, calcium, potassium, LDL, HDL, triglyceride, cholesterol. (Only at visit 2, 4 and 6)
- CAARS-S:S, CGI- -S (only for Visit 2), CGI- I (only for Visit 3 – 6), ADHD-RS-IV, E-SCT, C-SSRS and concomitant medication evaluation.
- AE/SAE evaluation
- Drug accountability

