8.3 Analysis of Efficacy and Safety

The efficacy measures are conducted on the per-protocol (PP) and intent-to-treat (ITT) basis. The per protocol will be defined as (1) The drug compliance is at least 80% (2) Subjects have completed data to determine the primary endpoint. (3) Subjects cannot have major protocol deviation. The major protocol deviation will be defined as (1) Inclusion or exclusion criteria not satisfied. (2) Not permitted concomitant medications (3) Wrong randomized treatment prescribed. An intent-to-treat (ITT) basis will be defined as the data are analyzed by the treatment groups to which the randomized patients who take at least one dose of study medication and have any post-baseline safety data collected. The safety measures are conducted on the patients who take at least one dose of study medication. The data are analyzed utilizing the last observation carried forward (LOCF) technique to impute the missing data.

The efficacy and safety information recorded on CRF will be summarized by tables presented in frequency and percentage for categorical variables, in mean with SD as well as median with the minimum and maximum for continuous variables. The comparison between three groups will be analyzed by nonparametric method as appropriate. All adverse events will be summarized with coding term, severity, relationship to study drug by frequency tables with the counts and percentage. In addition, serious adverse events will be listed with event narration.

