8.4 Premature Termination and Handling of Missing Data

Any premature termination of the study therapy will be recorded in CRF. Listing of the subjects with premature termination will be provided with the dates and reasons. Missing data caused by premature termination will be utilized the last observation carried forward (LOCF).

9. Quality Control and Quality Assurance

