Frequency table and change in ECG result will be summarized by center, visit and treatment. The transition of ECG is defined as following 4 groups: no change, change to normal, change to non-clinical significance, (NCS), change to clinical significance (CS).

6.7.7 *C-SSRS (Nilsson et al. 2013)*

Results of C-SSRS will be presented by center, visit, and treatment. The baseline of C-SSRS was set at screening visit (Visit 1).

The analysis for C-SSRS will follow the official guidance “Columbia-Suicide Severity Rating Scale - Scoring and Data Analysis Guide.” The 10 categories will be defined according to 10 binary responses (yes/no) on the C-SSRS.

Suicidal ideation is identified if the total score of the five suicidal ideation questions (Categories 1-5) >0 .
Suicidal behavior is identified if the total score of the five suicidal behavior questions (Categories 6-10) >0 .
Suicidal ideation or behavior is identified if the total score of the ten suicidal ideation and behavior questions (Categories 1-10) >0 .

Changes of suicidal ideation, suicidal behavior, and suicidal ideation or behavior from baseline during treatment will be summarized in a shift-table by visit, center and treatment.

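### Read as written, LOCF covers safety data, so a subject who stops before Week 8 is given a Visit 6 ECG copied from the pre-dose baseline and tabulated as no change

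*SAP*

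**What the plan says.** **The imputation rule.** LOCF appears three times with general scope.

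- SAP 6.8.1: "The data are analyzed utilizing the last observation carried forward (LOCF) technique to impute the missing data".
- Protocol 8.3, whose heading covers efficacy and safety together, gives the rule straight after the safety set: "The safety measures are conducted on the patients who take at least one dose of study medication. The data are analyzed utilizing the last observation", and so on.
- Protocol 8.4, on early termination: "Missing data caused by premature termination will be utilized the last observation carried forward (LOCF".

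SAP 6.6.1 repeats LOCF for the primary endpoint and prints a SAS step for it. SAP 6.7, the safety section, does not mention it.

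**The schedule.** Protocol Table 15 and the SAP 5.2.3 flowchart tick ECG at Visits 1 and 6. The treatment-visit list in Protocol 5.2.2 agrees: "ECG (Only at visit 6". Haematology and chemistry are at Visits 1, 2, 4 and 6, and Visit 2 may be skipped if it falls within 7 days of Visit 1. Follow-up Visit 7 has none of these tests. Protocol 4.5 has adverse-event withdrawals followed to an outcome but describes no assessments on leaving.

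**Baseline and output.** SAP 6.4 takes Visit 2 as baseline, or Visit 1 if there are no Visit 2 data. For ECG that means Visit 1. SAP 6.7.6 then reports shifts: "The transition of ECG is defined as following 4 groups: no change", plus shifts to normal, to not clinically significant and to clinically significant.

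**The concern.** A subject who stops before Week 8 has no scheduled on-treatment ECG. Carrying forward the last value means carrying forward the baseline, and comparing baseline with itself can give only one answer. The subject is then counted among those examined at Week 8 and found unchanged. Subjects who stop early may be the ones with a problem, so the error runs towards no harm.

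ECG change is a named safety endpoint. Protocol 1.2.2 reports a longer RR interval, lower heart rate and more sinoatrial arrest in dogs at 2500 mg/kg, and Protocol 1.4.1 says "The cardiovascular systems will be monitored in the clinical study". SAP 5.4 drops the between-arm tests after termination, so the descriptive tables are the main output and their denominators need to be real.

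**Working it through.** The plan gives no figure for dropout or for ECG abnormality, so there is nothing on this point to reproduce. (The design's stated 80% power does reproduce, at 0.801, in an exact calculation of one active arm against placebo at 40% versus 20%. Nothing below depends on it.)

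**Step 1. One dropout's ECG record.** Inputs: Visit 1 normal; Visit 6 missing; no ECG in between.

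| Rule | Visit 6 value | Table entry |
|---|---|---|
| LOCF as worded in Protocol 8.3, 8.4 and SAP 6.8.1 | Normal, carried from Visit 1 | No change |
| SAS step in SAP 6.6.1, run exactly as printed | Missing | None |
| LOCF limited to post-dose values | Missing | None |

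In the first row the carried value is the baseline value, so the entry is no change whatever the Visit 1 result was. The printed SAS step carries nothing because it clears the retained value at each new visit. That contradicts the SAP's own LOCF text.

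**Step 2. Laboratory values.** For a subject who leaves before Visit 4, the last value is from Visit 2 or Visit 1, which is the baseline. Carried value minus baseline = 0 at Visits 4 and 6. A subject who leaves between Visits 4 and 6 carries a real on-treatment value, so the exact-zero result does not apply.

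**Step 3. Who is in the table.** SAP 6.2 runs safety on the ITT set, which under SAP 5.3.1 needs one dose, eligibility and any post-baseline safety datum. One Visit 3 vital sign keeps an eligible dropout in. Protocol 8.3 asks only for one dose.

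**Step 4. Size.** Let n be the arm size, k the subjects who stop before Visit 6, and x the new abnormalities among those with a Visit 6 ECG. Observed rate = x/(n − k). Rate with carried baselines = x/n. Ratio = (n − k)/n. The dropout rate is an assumption, shown as a range.

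| Assumed dropout | n = 23 (stage I): k, ratio | n = 33 (both stages): k, ratio |
|---|---|---|
| 10% | 2, 21/23 = 0.91 | 3, 30/33 = 0.91 |
| 20% | 5, 18/23 = 0.78 | 7, 26/33 = 0.79 |
| 30% | 7, 16/23 = 0.70 | 10, 23/33 = 0.70 |

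**Step 5. If no abnormality is seen.** Both rates are 0%, and only the apparent precision differs. The one-sided 95% upper bound is 1 − 0.05^(1/n): 12.2% for 0/23, against 13.3% for 0/21, 15.3% for 0/18 and 17.1% for 0/16. These bounds are illustrative; for categorical data the SAP plans only frequencies and percentages.

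**Step 6. Physical examination.** The passages do not agree.

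| Place | Physical examination |
|---|---|
| Protocol Table 15 | Visits 1 and 6 |
| Protocol 5.2.2 list | Visits 2 to 6, without the visit limit that ECG and laboratory tests carry |
| SAP 5.2.3 flowchart | Visit 6 only |
| SAP 6.7.4 | Baseline at Visit 2 |

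Under Protocol 5.2.2 there are on-treatment examinations to carry. Under the SAP flowchart there is no earlier one at all. Neither schedule table has an examination at the stated baseline visit.

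**The case against.** The best reply is that the general sentence was never meant for ECGs. The SAP names LOCF for a specific endpoint only in 6.6.1; the safety section is silent on it and summarises by visit. The printed code carries nothing across visits, and a sensible analyst would not impute an ECG. This stands in part: the point concerns what the rule produces as written, not a known result. But silence in the safety section does not override three general statements, one of them placed directly after the safety set. The code sits under the primary endpoint and looks like a coding slip, so it is no safeguard.

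The clinical stake can also be overstated. The dog findings were at 2500 mg/kg, and Protocol 1.4.1 describes the blood-pressure and heart-rate changes as mild and not clinically significant. Phase I ECGs were normal throughout. Vital signs and adverse events are assessed at every treatment visit, clinically significant abnormal findings are recorded as adverse events, and early terminations are listed with dates and reasons. All of this stands. Early stoppers are not invisible, but the ECG shift table would still be wrong about them.

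The dropout range is assumed. The only withdrawal figure in the documents is 0 of 6 in the open-label Part I.

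A reader might infer three stronger things that the documents do not support:

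- **That physical examinations are likewise no change by construction.** That needs Table 15 together with a Visit 1 baseline, and the other passages contradict both.
- **That LOCF would produce a 0% ECG abnormality rate whatever the truth.** If every change occurred in subjects who stopped early, an observed-data table would also show 0%, because those ECGs do not exist. That is missing data, not LOCF.
- **That adding assessments at withdrawal would repair this trial.** SAP 5.4 says the study was terminated, so no such data can now be collected.

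**Conclusion.** The point holds for ECG, and for laboratory values in subjects who leave before Visit 4. Taken literally, the rule enters a pre-dose value as a Week 8 observation, overstates the number assessed, and multiplies the observed rate of new ECG abnormality by about 0.9 to 0.7 if 10% to 30% of an arm stops early. The direction follows from the text; the size rests on the assumed dropout and on LOCF being applied to safety tables as worded. It is worth correcting because a stated rule yields a wrong table, but it concerns descriptive safety output in a terminated proof-of-concept trial. No conclusion on carried-forward physical examinations is possible until the conflicting passages are reconciled.

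**What to change.** In SAP 6.8.1, and for consistency in Protocol 8.3 and 8.4, limit LOCF to the efficacy scales. Report ECG, laboratory, vital-sign and physical-examination changes on observed post-dose data, with the number actually assessed at each visit as the denominator. Since the study has ended, the practical place is the SAP and the tables of the clinical study report.

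The cost is wording and smaller stated denominators. The change does not recover the missing ECGs or remove bias from informative dropout; it only stops them being shown as measured.

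Separately, reconcile Protocol Table 15, Protocol 5.2.2, the SAP 5.2.3 flowchart and SAP 6.7.4 on when physical examinations take place and which one is baseline.

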6.8.2 Multiple Comparisons / Multiplicity

No multiple comparison will be applied in performing statistical analysis.

7. DATA HANDLING PROCEDURE

7.1 Data Storage and Analysis

All data are stored in the VCRO EDC Lite system.

Statistical evaluation will be performed using SAS 9.4 (SAS-Institute Inc.) and Microsoft 365 Excel 2402.

8. APPENDICES

8.1 Table of Contents (TOC) for Tables, Figures and Listing

Refer to section 14 and 16.2 in clinical study report.

[figure not shown]
No further SAP amendment will be required for the deviation of TOC when the changes are still complied with the main text SAP.

8.2 Version Control Information of SAP

Document	Version	Approved date
Final	20240425_00	April 25, 2024

